9.6 Independent Data Monitoring Committee

As suggested by international guidelines on data monitoring committees, an independent Data Monitoring Committee (DMC) will be formed to decide whether the predefined criteria for early stopping of the trial are met.^{46,47} The DMC will meet at the interim analysis to be performed after 73 and 146 subjects and at the end of study. In the event of new unanticipated and related adverse effects being reported, the DMC will convene for an unscheduled meeting and will determine at that time the need for additional review and or action.

The Data Monitoring Committee will consist of three to five independent experts outside of the study group. These members:

- will not be involved in the conduct of the clinical trial
- will not have any financial interest in the outcome of the study
- will have no planned authorship in publications on study results
- will not serve in parallel on the DMC of a clinical trial with diabetic patients with a different sponsor

10 DATA HANDLING

10.1 Quality Assurance and Quality Control of Data

The Investigator will permit trial-related monitoring, audits, IRB/Ethics Committee review, and regulatory inspection(s), provide direct access to source data and documents by suitably qualified and authorized persons from AOTI, Ltd. (and their representatives) and/or the bodies stated above.

The Investigator will obtain the prior written consent of the subject for such direct access. AOTI Ltd. will conduct a site visit to verify the qualifications of each Investigator, inspect the site facilities, and inform the Investigator and all trial staff of their responsibilities and the procedures for ensuring adequate and correct documentation.

The Investigator is responsible for ensuring the accuracy and credibility of the data by ensuring that a process is in place for the review of completed CRFs prior to any inspection by the study monitor.

10.2 Case Report Forms and Source Documents

All study data will be recorded in a Case Report Form. Source data will not be recorded directly onto the CRF with the exception of the EQ-5D and CWIS. Data from source documents such as paper medical records or original electronic reports shall be signed and dated by a member of the study team and must be available in the subject's file.

All Case Report Forms (CRFs) are to be completed by site personnel delegated responsibility by the Investigator and reviewed and signed by the Investigator. All data recorded in the CRFs must be consistent with the subject's source documents. Entries in the CRF for each subject will be checked against the source documents at site by the study monitor. Missing or un-interpretable data will be discussed with the Investigator for resolution.

The database used for the compilation and storage of CRFs is the property of AOTI Ltd. and will be retained by AOTI Ltd. at the end of the trial. A copy of CRF data will be retained by each site in the provided Investigator Site File.

10.3 Direct Access to Source Data

The Investigator will permit trial-related monitoring, audits, IRB/Ethics Committee review, and regulatory inspection(s), providing direct access to source data and documents by suitably qualified and authorized persons from AOTI Ltd. (and their representatives) and/or the bodies stated above.

The Investigator will obtain the prior written consent of the subject for such direct access. During the trial a study monitor representing AOTI Ltd. will regularly visit the trial site to review protocol compliance, verify entries in the CRFs with source data in the subject's medical records and ensure the trial is being conducted in accordance with the regulatory and ICH GCP requirements.

The Investigator assures the Sponsor of the necessary support at all times.

10.4 Documentation of Subject Participation

For all subjects who give written informed consent regardless of whether they receive TWO2 therapy or control therapy, the Investigator must record subject identification data in the "Subject Identification List" (full name, initials, date of birth, subject identification code). The

Subject Identification List must allow for the definite identification of any subject that takes part in the trial. The Investigator must keep the list of subject identification codes until informed in writing by the Sponsor that the list can be destroyed.

A statement acknowledging the participation of a subject in this clinical trial must be documented in the subject's medical file/notes and, where the trial physician is not the primary care physician, it is recommended that the subject's primary care physician is informed of the subject's participation in this clinical trial, provided the subject gave his/her consent.

10.5 Essential Documents for the conduct of a Clinical Trial

At the beginning of the trial, an Investigator Site File will be established at the trial site. The Investigator is responsible for maintaining the trial documents and must take measures to prevent accidental or premature destruction of these documents.

The essential documents to be included in the Investigator Site File are listed in ICH E6 Section 8.

10.6 Archiving Trial Documents

All trial documents belonging to the Investigator Site File will be archived at site (or off-site at a suitably secure location meeting ICH GCP requirements if specified and agreed in writing by the Sponsor) for a period of 15 years from the date of overall closure of the trial. This date will be communicated to all sites by the Sponsor at the end of the trial. A written record of the location of archived documents is to be forwarded to the Sponsor by each centre at the end of the trial (e.g. in the study closure report).

All trial documents belonging to the trial master file will be archived by the Sponsor at a suitably secure location meeting ICH GCP requirements, for a period of 15 years from the date of overall closure of the trial.

11 ETHICS, LEGAL AND ADMINISTRATIVE ASPECTS

11.1 Approval of Trial Documentation

All trial related documentation must be approved by AOTI Ltd. and Principal Investigator, in writing, before it is released. Prior to initiation of the trial, the protocol, informed consent form, subject information sheet and any other relevant trial documentation will be submitted to the responsible IRB/Ethics Committee and Regulatory Authorities. Written approval of the trial must be obtained and forwarded to AOTI Ltd. before the trial center can be initiated or trial materials released to the investigator.

Furthermore, any necessary extension or renewal of the IRB/Ethics Committee approval must be obtained and forwarded to the sponsor. In particular, change(s) to any aspect of the trial, such as modification(s) of the protocol, the written informed consent form, the written information provided to subjects, and/or other procedures must be approved, in writing, by the IRB/Ethics Committee.

The Investigator will report promptly to the IRB/Ethics Committee, any new information that may adversely affect the safety of subjects or the conduct of the trial. Similarly, the Investigator will submit written summaries of the trial status to the IRB/Ethics Committee annually, or more frequently, if requested by the IRB/Ethics Committee. Upon completion of the trial, the Investigator will provide the IRB/Ethics Committee with a brief report of the outcome of the trial, if required.

11.2 Ethical Conduct of the Trial

11.2.1 Good Clinical Practice

The procedures detailed in this protocol are designed to ensure that the Sponsor and Investigator abide by the principles of the Good Clinical Practice guidelines of the International Conference on Harmonization (ICH).

11.2.2 Declaration of Helsinki

The trial will adhere to the guidelines of the World Medical Association Declaration of Helsinki in its revised edition (Fortaleza, Brazil, October 2013), as well as the demands of national drug/medical device and data protection laws and other applicable regulatory requirements. A copy of the Declaration of Helsinki is supplied in the Appendices (Appendix II).

11.3 Subject Information and Consent

The Investigator is responsible for ensuring that no patient is subjected to any trial-related examination or activity before that patient has given informed consent. Written consent must be given by the patient/their legally authorized representative after the receipt of detailed information. The verbal explanation will cover all the elements specified in the written information provided for the patient.

The Investigator will inform the patient of the aims, methods, anticipated benefits and potential hazards of the trial including any discomfort that it may entail. The patient must be given every opportunity to clarify any points he/she does not understand and if necessary, ask for more information. At the end of the interview the patient may be given time to reflect if this is required, or if the patient requests more time. Patients will be required to sign and date the informed consent form. After completion, informed consent forms will be kept and archived by the Investigator in the Investigator's trial master file.

It should be emphasized that the subject is at liberty to withdraw their consent to participate at any time, without penalty or loss of benefits to which the subject is otherwise entitled. Patients who refuse to give, or who withdraw written informed consent will not be included or continued in the trial.

11.4 Insurance

The company carries insurance to cover the use of the products for the devices for the indications defined in this trial.

11.5 Amending the Protocol

No substantial amendment or deviation should be implemented without agreement from the sponsor and prior review and documented approval/ favorable opinion from the IRB/Ethics Committee and Regulatory Authorities except where necessary to eliminate an immediate hazard(s) to trial subjects. In such case, as soon as possible, the implemented deviation or change, the reasons for it, and if appropriate, the proposed protocol amendment(s) must be submitted to AOTI Ltd. for approval and then submitted to the IRB/Ethics Committee and Regulatory Authorities for approval.

When an amendment is thought to be non-substantial, it must be confirmed by AOTI Ltd. and the Investigator in advance, in writing, and the reason for the non-substantial amendment must be documented by both the Investigator and the Sponsor.

11.6 Data Protection

To protect the subject's identity, a unique subject identification code (subject ID) will be assigned by the Investigator to each trial subject and used in lieu of the subject's name when the Investigator reports AEs and/or other trial related data. Thus, the subject identification code, and not the subject's name or hospital number, will appear on all documents.

Personal information will be treated as confidential, but may need to be reviewed by monitors from AOTI Ltd., auditors and authorized representatives of the IRB/Ethics Committee and Regulatory Authority. The subject's consent to direct access to the subject's original medical records for data verification purposes has to be obtained prior to that patient's participation in the trial.

Documents which identify the subject (e.g. signed consent forms) must not be submitted to the sponsor at the end of the trial, but must be maintained in confidence by the Investigator.

11.7 Financial Aspect of the Trial

The Sponsor, AOTI, shall provide payment for this study in accordance with the following schedule:

- 1) The Sponsor will pay all fees for Institutional Review Board / Ethics Committee approval fees
- 2) The Sponsor will reimburse directly all study related costs for TWO₂ medical devices, dressings, and Salvatelli off-loading boot

11.8 Disclosure of all Information and Results

In signing the final protocol, the Investigator agrees to keep all information and results concerning the trial confidential for as long as the data remains unpublished. The confidentiality obligation applies to all personnel involved at the investigational site.

Publication of trial results requires prior approval from AOTI Ltd.

11.9 Declaration of the End of Trial

The Investigator is responsible for notifying the IRB/Ethics Committee of the end of the trial, within 90 days of its completion. AOTI Ltd. is responsible for notifying the competent authority of the end of the trial, within 90 days of its completion.

If the trial ends prematurely the IRB/Ethics Committee and the competent authority must be informed within 15 days.

11.10 Clinical Trial Report

AOTI Ltd. is responsible for the writing of the clinical trial report. The format of the report will be in accordance with the ICH GCP guidelines (E3).

11.11 Publication plan

It is planned to publish the main paper of this trial in a premium journal like The Lancet, New England Medical Journal or Diabetes Care.

Secondary analyses will be published depending on subject and clinical relevance.

11.12 Study Schedule

Study Start Date: July 2014

Estimated First Interims Analyses: January 2017

Estimated Second Interims Analyses: May 2017

If needed Final Analyses: December 2017

Reporting/Submission date: 6 month after data analyses

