9 STATISTICAL ANALYSIS

9.1 Sample Size and Power Analysis

All sample size estimations in this section of the protocol were undertaken using the sampsi function in Stata 11 (Statcorp LP, Texas, USA). Comparisons of groups was made assuming no continuity correction.

Little data are available on similar studies using topical oxygen therapy within randomized clinical trials making sample size estimation problematic. Large trials of dermal substitutes and negative pressure have been undertaken that can be used to indicate the potential healing in the control group. The three large trials have control healing of between 18% and 28.9% around 12 weeks after entering the trial, with a mean of 28%.^{25,27,29}

The expected improvement in healing using the active device is more problematic as there have been few comparative studies published. Aburto and Frye undertook a randomized study of 20 venous ulcers and 20 diabetic foot ulcer patients.⁴² Topical oxygen demonstrated higher healing in the DFU patients after 90 days of 90% versus 40% in the control group. Blackman et al randomized 28 patients with DFUs and obtained a similar response (82.4% versus 45.5%).²² The potential difference between treatment groups was therefore 50% and 36.9% respectively. Using these studies a total sample size of 28 and 52 would be expected based on 80% power at the 5% level of significance. Neither of these studies was blinded. It is therefore likely that the effect is likely to be substantially smaller than that experienced in these two studies.

Because of the small size of these trials and lack of blinding it has been decided to offer a more cautious approach to the calculation of sample size based on a smaller expected benefit of oxygen therapy. By combining the results of the two randomized studies already undertaken the control group achieved a healing rate of 9/21 (42.8%). In the actively treated group healing occurred in 23/27 (85.2%). Assuming an expected control rate of 43% and a difference of half that experienced in these trials of 21% (to 64%) would require a sample size of 88 patients in each group (total=176), with a power of 80% and a level of significance set at $p<0.05$.

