In order to overcome the uncertainty surrounding the expected benefit, the trial will be undertaken using group sequential design (GSD) allowing for interim analysis to be performed at intervals during the trial recruitment. The interim analysis will take place after one third of subjects have been recruited, after two thirds and then a final analysis at full recruitment. The Pocock method of interim analysis will be used, which requires an equal level of significance ($p<0.022$) over the three analyses.⁴³ If the difference in primary outcome produces a probability less than this in any of the analyses then the null hypothesis is rejected and the alternative hypothesis of a difference in healing has been shown. In order to achieve this level of significance a total of 110 patients need to be recruited to each arm of the trial (total=220).

Since all patients will achieve a 12 week end point (healed versus unhealed) no uprating of this sample size will be made to take into consideration patients lost to follow up (see section 9.2).

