9.2 General Statistical Methods

Analysis Populations

Two analysis populations will be evaluated: Intent To Treat (ITT) and Per Protocol (PP). The ITT population will be considered the primary population of interest and will include all subjects who were randomized to study treatment. The PP population will include all subjects who were randomized to study treatment and had no significant protocol violations that might affect the outcome of treatment.

All participants will be followed up to the primary end point (12 weeks) irrespective of whether they were on active treatment. Participants that withdraw from treatment continue to be followed up to the 12 week end-point. Participants that die, undergo amputation or who are lost to follow up will be considered as treatment failures.

Continuous demographic variables (age, ulcer duration, etc.) will be summarized for the study population as descriptive statistics (number, mean, median, SD, minimum and maximum value), and by randomized groups. No formal inferential statistical testing will take place of baseline values in relation to randomized groups.

Categorical demographic variables, such as gender, will be summarized as a proportion of the intention-to-treat population.

All analyses will be undertaken using the STATA 11 statistical package.

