9.3 Primary outcome analysis

The primary endpoint is the “Incidence of complete wound closure within 12 weeks”.

The null hypothesis to be tested is that there is no difference between treatment groups in terms of the rate of wound healing after 12 weeks of study treatment. The alternative hypothesis is that such a difference exists.

Uncorrected Chi squared analyses will be used to determine the difference between treatment groups in terms of wound closure rate within 12 weeks, at the interim analysis. 95% confidence intervals will be estimated using the normal approximation interval.

Logistic regression analysis will be used to determine the effects of confounding on the primary outcome at the trial end. In particular, gender, age, ulcer duration, size and diabetic factors will be considered in the model. A stepwise procedure will be used to eliminate non-significant covariates from the model. The effect of different centers' outcomes will be entered as a random effect into the model.

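### After an early stop the plan schedules no primary comparison on the full intention-to-treat set, and does not say how outcomes still pending at the look are used

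*Combined protocol and SAP*

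**What the plan says.** Section 9.1 sets two interim analyses and "then a final analysis at full recruitment", using the Pocock method, "which requires an equal level of significance ($p<0.022$) over the three analyses". It adds: "If the difference in primary outcome produces a probability less than this in any of the analyses then the null hypothesis is rejected". The schedule in section 11.12 gives January 2017 for the first look, then "Estimated Second Interims Analyses: May 2017", then "If needed Final Analyses: December 2017". The report is due six months after the data analyses.

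Section 9.2 makes ITT the primary population, which "will include all subjects who were randomized to study treatment", and follows every participant to week 12 whether or not they are still on treatment.

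Section 9.3 assigns the uncorrected chi-squared test to the interim analysis, and a logistic model with covariates and a random centre effect to the end of the trial. Section 9.5 drops subjects with missing data from the analyses concerned.

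The trigger for a look is stated in two ways. In the Synopsis it is one third, then two thirds, of subjects having completed 12 weeks. In sections 3.1 and 9.1 it is one third, then two thirds, having been recruited.

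**The concern.** The primary outcome takes at least 12 weeks to observe. When a look is read, some subjects have been randomised but have no outcome yet. They belong to the primary ITT set, and their follow-up continues. If the look crosses the boundary, the null is rejected there and the only later analysis of the primary endpoint in the schedule is one that may not be needed. No section says whether the chi-squared comparison is repeated when the remaining outcomes mature, which estimate is then the trial's result, or which dataset the end-of-trial model uses.

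An estimate taken at a boundary crossing is too large on average. Outcomes that mature afterwards are not selected in that way and pull it back towards the truth. If they are not analysed, the published difference is larger than the trial's own data support, and the population analysed is not the one section 9.2 calls primary.

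**Working it through.** **Inputs**
- From section 9.1: 43% control and 64% active, 80% power, no continuity correction, 0.022 at each of three looks. The test is two-sided because section 9.3 says "The alternative hypothesis is that such a difference exists".
- From section 9.6: looks after 73 and 146 subjects. From section 9.1: 220 in total.
- Pace: 73 subjects in about 6 months (Synopsis), or 73 between the January and May 2017 looks (section 11.12).
- Outcome lag: 84 days for a wound still open at week 12, and up to 98 days for one that closes late and must be confirmed 2 weeks on (sections 3.3.1 and 8.2.7).
- Assumptions: the look is triggered by completed 12-week outcomes (Synopsis), recruitment is even and does not pause while a look is prepared, and allocation is 1:1.

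**1. The plan's own figures**

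n per arm = [z(α/2)·√(2·p̄·q̄) + z(0.80)·√(p1q1 + p2q2)]² / (p2 − p1)², with p̄ = 0.535, 2p̄q̄ = 0.4976 and p1q1 + p2q2 = 0.4755.
- α = 0.05: (1.960×0.7054 + 0.842×0.6896)² / 0.0441 = 87.4, so 88. This matches the plan.
- α = 0.022: (2.290×0.7054 + 0.842×0.6896)² / 0.0441 = 109.3, so 110. This matches the plan.
- Three equally spaced looks at 0.022 give an overall two-sided error of 0.0496 by simulation.

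**2. Subjects pending at a look** = pace × lag (84 days = 2.76 months; 98 days = 3.22 months)

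| Pace | Per month | 12-week lag | 14-week lag |
|---|---|---|---|
| Synopsis: 73 in 6 months | 12.2 | 34 | 39 |
| January to May 2017: 73 in 4 months | 18.3 | 50 | 59 |
| May to December 2017: 74 in 7 months | 10.6 | 29 | 34 |
| July 2014 to January 2017: 73 in 30 months | 2.4 | 7 | 8 |

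Counting days from mid-January to mid-May (120), the second row is 73/120 × 84 to 98 = 51 to 60. The third row is the relevant one for look 2. The last row cannot describe recruitment around look 1 if the May 2017 date is to be met.

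**3. The estimate when look 1 stops the trial** (one million simulated trials, 37 active and 36 control, uncorrected chi-squared, stop for benefit at two-sided p<0.022)
- At 43% v 64%, 29.5% of trials stop, with a mean observed difference of 34.3 points against a true 21. The excess is 13.3 points.
- The cause is the height of the boundary. Near the planned rates, crossing needs about 2.290 × √[0.535×0.465×(1/37 + 1/36)] = 0.267, or 27 points.

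**4. Adding m pending subjects**

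These outcomes are unselected, so the mean becomes about (73×34.3 + m×21)/(73 + m).
- m = 34: (2503.9 + 714)/107 = 30.1
- m = 60: (2503.9 + 1260)/133 = 28.3

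Direct simulation gives 30.1 at 34 and 28.4 at 59. Inclusion removes 4 to 6 of the 13.3 excess points and leaves 7 to 9.

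Among these stops, the full set no longer reaches p<0.022 in about one case in ten (11.4% with 34 added, 10.1% with 59).

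**5. Other cases**
- First stop at look 2 (146 subjects): 35.0% of trials, mean 23.8 points, an excess of 2.8.
- If the truth were 43% v 53% (an assumed weaker effect): look 1 stops in 6.9% of trials with a mean of 32.3 points. This falls to 25.2 with 34 pending subjects added and 22.3 with 59, against a true 10.

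**The case against.** The strongest reply is that section 11.12 is an administrative calendar with estimated dates and defines no analysis set. On that view the conditional wording refers only to the third look at 220, which is unnecessary if an interim has already stopped the trial. Several sections support this reading: ITT is primary and everyone is followed to week 12 (9.2), a model is planned for the end of the trial (9.3), the end of the trial is the last subject's 38-week follow-up (8.2.10), follow-up is assured after premature termination (8.2.11), and the monitoring committee also meets at the end of the study (9.6).

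Much of this stands. A reader might infer that, after a stop, the result rests on the 73 subjects at look 1 and the others are left out. The documents do not say so, and section 9.2 points the other way. But none of these sections schedules the primary comparison on the completed ITT set, and the end-of-trial model in section 9.3 has no stated dataset after a stop. The gap is one of silence and conflicting signals.

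Three further inferences go too far:
- That as many as about 75 subjects would be pending. This needs extreme dates within months given only as estimates, or a lag longer than 14 weeks. The Synopsis pace gives 34 to 39.
- That leaving subjects out causes the overstatement. The cause is selection at the boundary. Omission only fails to dilute it.
- That the look-1 excess is typical of any early stop. At look 2 it is about 3 points.

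The trigger also matters. If a look occurs when one third are recruited, as in sections 3.1 and 9.1, the subjects without outcomes are among the 73 themselves, and section 9.5 read literally would drop them. That reading needs a rule too.

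**Conclusion.** The point holds as a gap in the plan. After an early stop no primary comparison is scheduled on the full ITT set, and nothing says how outcomes maturing later are analysed or reported. Under the planned effect, with the look taken at 73 subjects who have completed 12 weeks, about 34 to 39 randomised subjects would be pending at look 1 at the Synopsis pace, and about 50 to 60 at the pace implied by the 2017 dates. A look-1 stop, in about 30% of trials, reports about 34 points on average against a true 21. Including the pending subjects brings this to about 28 to 30, so more than half of the excess remains.

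These counts rest on even, uninterrupted recruitment, and the estimates on the planned rates. Type I error is not in question, because the decision to reject stays with the look. The clarification should be made before the first look is read.

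**What to change.** In sections 11.12 and 9.1, replace the conditional final analysis with a statement that, after an early stop, the primary ITT analysis is always run once every subject randomised by the stopping date has reached week 12 and any closure confirmation. State that:
- the decision to reject rests with the look that crossed p<0.022 and is not reopened if the full-set p-value is larger;
- the full-ITT difference, its interval and the adjusted model of section 9.3 are reported beside the look's own estimate;
- both estimates remain subject to early-stopping bias.

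Reconcile the look trigger between the Synopsis (completed 12 weeks) and sections 3.1 and 9.1 (recruited), and say how subjects without an outcome at a look are handled in view of section 9.5.

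The cost is a few sentences, with no extra subjects or visits. After an early stop the report waits up to about 14 weeks, and the reported difference will usually be smaller.
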